## 9.7 Efficacy Analyses

The efficacy analyses will focus on anti-tumor response (primary and secondary endpoints) after treatment with tipifarnib in the mITT analysis set of the AIM-HN. The sensitivity efficacy analyses will be performed in the per-protocol analysis set.

### 9.7.1 Primary Endpoint

The count and proportion with confirmed OR by IRF for subjects with high VAF will be presented in the mITT analysis set as primary analysis. The estimate of the ORR will be calculated using the maximum likelihood estimator for the proportion of tipifarnib treated subjects whose Best Overall Response is

confirmed CR or confirmed PR as assessed by IRF. The exact (Clopper-Pearson) 95% confidence interval (CI) for the proportion will also be presented.

The above analysis will be repeated in the per-protocol analysis set and all VAF population. The ORR based on investigator's assessment will also be summarized.

## 9.7.2 Key Secondary Endpoints and Other Secondary Endpoints for AIM-HN

DOR, PFS, and OS will be summarized using the Kaplan-Meier (KM) ([Kaplan and Meier 1958](#)) estimates in the AIM-HN mITT analysis set, which may also be summarized in the PPS. The 50% quartile (median) and 2-sided 95% confidence interval time to event endpoint will be calculated by the Brookmeyer and Crowley method ([Brookmeyer R and Crowley JJ, 1982](#)) with log-log transformation. The 6-month and 9-month progression-free survival rate, and 12-month survival rate will be estimated as well. A KM plot for each endpoint will be presented as applicable.

TTR will be summarized descriptively by summary statistics.

Response related efficacy endpoints, including TTR, by independent review facility and investigator assessment will also be summarized.

These analyses will be repeated for high VAF subjects and all VAF subjects.

### 9.7.2.1 Quality of Life (QoL)

The analysis window for QoL analysis for each scheduled visit are listed in Table .

**Table 2: QoL Analysis Window**

Scheduled Visit	Target Day	Analysis Window
Baseline	Day 1	From Day -28 to Day 1
Cycle 2 Day 1	Day 29	From Day 2 to Day 42
Cycle n Day 1	Day 28 x (n-1) + 1	From Day 28n-41 to min {Day 28n-14, last dose date-1}
End of Treatment	Day 30 after the last dose	>= last dose date

Note: Study days are relative to Cycle 1 Day 1.

If a subject has more than one questionnaire collected in an analysis window, the one closest to the target day will be selected; if multiple questionnaires have the same distance in days from the target date, the later one will be selected; if the multiple questionnaires are collected on the same date, the worst one will be selected.

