20. CT scan with a contrast agent is the preferred imaging method and the same technique should be used at baseline and post-treatment assessments. CT scan coverage at screening should encompass scans of the neck (including the skull base), chest and abdomen (including the liver and adrenals). Any other areas of disease involvement should be scanned based on the subject's signs and symptoms. If subjects are allergic to IV contrast, MRI scans or non-contrast CT may be used. Subjects with contrast allergy or renal insufficiency may use non-contrast CT or MRI, whichever is required to adequately assess all disease. The one exception where MRI would not be recommended is for the evaluation of parenchymal lung metastases. In this instance, CT would be preferred. If imaging of the brain is indicated, MRI of the brain with and without gadolinium should be performed for optimal evaluation of the brain. If MRI is medically contraindicated, CT of the brain with and without contrast would be suggested. Guidelines for imaging and instructions for transmission of the images to the IRF will be provided to each study site.
21. CT scans will be performed at least once approximately every 8 weeks (\pm 5 days) for 12 months, thereafter once approximately every 12 weeks (\pm 5 days) until disease progression. The imaging schedule (every 8 weeks or every 12 weeks) should be maintained regardless of dosing delays or additional imaging assessments performed.
22. Scans at the End of Treatment visit: Applies only for subjects who terminated treatment for reasons other than disease progression. In these subjects, imaging should be performed at the End of Treatment visit if not done within the prior 8 weeks or if a tumor assessment is required for the confirmation of response.
23. Subjects who discontinue treatment for reasons other than disease progression should continue tumor assessments until disease progression. Tumor assessments may continue upon initiation of another anticancer therapy unless withdrawal of subject's consent to study procedures.

[REDACTED]

[REDACTED]

[REDACTED]

[REDACTED]

[REDACTED]

[REDACTED]

[REDACTED]

[REDACTED]

[REDACTED]

[REDACTED]

28. Subjects will receive tipifarnib starting at 600 mg orally bid with food on days 1-7 and 15-21 of 28-day treatment cycles.

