9.2.5 Day 1 (\pm 2 days) of Cycle 3 and Beyond

The following procedures will be performed at this visit:

- Collection of weight and vital signs (heart rate, blood pressure, temperature)
- ECOG performance status
- Symptom based physical examination
- Completion of Quality of Life assessment questionnaires
- Laboratory Tests: Fasting not required.
 - Serum Chemistry
 - Hematology
 - Serum/urine pregnancy test for females of child-bearing potential only

■ [REDACTED]

■ [REDACTED]

■ [REDACTED]

- Concomitant medications
- Assessment of AEs

In addition to the above procedures, the clinical site will conduct a drug accountability review on the returned empty bottles and unused medications and will also review the dosing diaries to assess compliance with the dosing schedule.

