**Figure 2: AIM-HN Design**

All subjects must have measurable disease that meets the criteria for selection as a target lesion according to RECIST v1.1 and presence of at least measurable target lesion by local radiology prior to enrollment is required. HNSCC diagnosis will be by local laboratory. All AIM-HN enrolled subjects must have a known missense HRAS tumor mutation based on centralized testing or other HRAS test used by the trial site that has been approved by Kura Oncology, Inc.

AIM-HN enrolled subjects will receive treatment with tipifarnib until disease progression, unacceptable toxicity or any criteria for withdrawal from the trial or treatment occurs. Tipifarnib will be administered with food at a starting dose of 600 mg, orally, bid on days 1-7 and 15-21 of 28-day treatment cycles. Stepwise 300 mg dose reductions to control treatment-related, treatment-emergent toxicities may occur.

Tumor assessment for the primary analysis will be performed by IRF according to RECIST v1.1 and provided to the IDMB. Investigator assessment of tumor response will also be collected and reported as a supportive analysis. Tumor response assessment should occur approximately every 8 weeks ( $\pm 5$  days) for the first 12 months; thereafter, tumor response assessment should occur approximately every 12 weeks ( $\pm 5$  days) until disease progression. The tumor response assessment schedule (every 8-12 weeks) should be maintained regardless of dosing delays or additional imaging assessments performed. Upon disease progression, all subjects will be followed approximately every 12 weeks for survival and the use of subsequent therapy until either death or End of Study (up to 2 years after the enrollment of the last study subject, see [protocol Section 6.7.1](#)), whichever occurs first. All subjects will be followed-up for safety through the End of Treatment visit which occurs approximately 30 days after treatment discontinuation or immediately before the administration of another anticancer treatment, whichever occurs first. Additional safety follow-up may be conducted if unresolved toxicity is present at this End of Treatment visit.

[figure not shown]

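### From Cycle 3 on, the quality-of-life window keeps a Day 1 questionnaire only if the subject is dosed on a later day, so by-visit means leave out subjects who stop at that visit

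*SAP*

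**What the plan says.** SAP Section 9.7.2.1, Table 2, sets the analysis windows for quality of life:

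- Cycle 2 Day 1: target Day 29, window "From Day 2 to Day 42", with no reference to the last dose.
- Cycle n Day 1 for later cycles: target Day 28(n-1)+1, window "From Day 28n-41 to min {Day 28n-14, last dose date-1" (closing brace follows).
- End of Treatment: target "Day 30 after the last dose", window ">= last dose date".

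If a window holds several forms, "the one closest to the target day will be selected". A tie in distance goes to the later form.

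Protocol Section 9.2.5 lists "Completion of Quality of Life assessment questionnaires" among the procedures of the Day 1 visit (± 2 days) for Cycle 3 and beyond. SAP Section 5.1 gives dosing as "bid on days 1-7 and 15-21 of 28-day treatment cycles". Protocol Section 9.2.7 places the End of Treatment visit, which includes the questionnaires, about 30 ± 7 days after the last dose, or just before another anticancer drug if that is sooner.

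The windows feed the summaries of actual value and change from baseline at each post-baseline visit for four QLQ-H&N35 scales (Pain, Swallowing, Speech, Senses) and for EQ-VAS.

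**The concern.** Membership of the Cycle n summary depends on what happens after the questionnaire is completed. A form belongs to a scheduled Day 1 visit, but the rule keeps it there only when the subject is dosed again on a later day. The decision to continue or stop is taken at or after that visit and is likely to be related to how the subject is doing. The by-visit mean is then a mean over those who went on, not over those who attended and answered.

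The table is also inconsistent. A subject who answers at Cycle 2 Day 1 and stops is kept in Cycle 2; one who does the same at Cycle 3 Day 1 is not kept in Cycle 3. The SAP gives no reason.

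Quality of life is a listed secondary objective in both documents. The trial has a single treated arm, so no comparator with the same selection offsets it.

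**Working it through.** **Inputs.** Windows, targets and selection rule: SAP Table 2. Dosing days: SAP Section 5.1 and Protocol Table 2, footnote 28. Visit timing: Protocol Sections 9.2.5 and 9.2.7.

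**Reproducing the table.** With n = 2 the general formulas give a target of 28(2-1)+1 = Day 29 and an upper end of 28×2-14 = Day 42, both as printed in the Cycle 2 row. The Cycle 3 lower end is 28×3-41 = Day 43, contiguous with Day 42. The cap is the only term that the Cycle 2 row lacks.

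**A subject who completes the form at Cycle n Day 1 and takes no further dose, on schedule:**

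- Last planned dose: 28(n-2)+21 = Day 28n-35.
- Window end: min(28n-14, 28n-36) = Day 28n-36.
- Target: Day 28n-27, which is 9 days after the window has closed.

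| n | Target | Window without cap | Last dose | Window with cap |
|---|---|---|---|---|
| 3 | 57 | 43–70 | 49 | 43–48 |
| 4 | 85 | 71–98 | 77 | 71–76 |
| 5 | 113 | 99–126 | 105 | 99–104 |

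For n = 3 to 8, none of the five permitted visit days (target ± 2) lies inside the capped window. Without the cap all five do (Days 55–59 for Cycle 3).

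**General statement.** A form on or after the last dose date is later than the last dose date minus 1, so it cannot lie in any Cycle n window with n ≥ 3. A search over n = 3 to 14, last dose Days 1 to 499 and forms 0 to 59 days after the last dose found no exception, so dosing delays do not rescue it. A dose on the visit day alone does not help either: a last dose on Day 57 puts the cap at Day 56.

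**Where the form goes.** It enters End of Treatment, whose target is 28n-35+30 = Day 28n-5. An on-target Day 1 form is 8 days after the last dose and 30-8 = 22 days from that target (20 to 24 days with ± 2). A form from an End of Treatment visit at 30 ± 7 days is at most 7 days away and is selected, so the Day 1 form then enters no by-visit summary. If no other form exists, the Day 1 form is reported as End of Treatment.

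**Cycle 2 comparison.** Last dose Day 21, form on Day 29: inside Days 2–42, so it is kept in Cycle 2. It also satisfies the End of Treatment window, so one form can qualify twice.

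**Size.** If a share p of attenders is excluded and scores d points worse than the rest, whose mean is m, the mean over all attenders is (1-p)m + p(m-d) = m - pd. The reported mean is too favourable by p×d. Neither p nor d is in the documents. Assuming p = 0.10: d = 5, 10 and 20 give 0.5, 1.0 and 2.0 points. Assuming p = 0.20 and d = 10: 2.0 points.

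**The case against.** The strongest defence is that the cap is a deliberate split between on-treatment and post-treatment records. SAP Section 7.1 counts a cycle as initiated only if a dose above 0 mg was given, and Protocol Table 2, footnote 34, describes collection as monthly on treatment and at End of Treatment. On that view a subject never dosed in Cycle n did not start it. This explains a possible motive but does not rescue the rule. The protocol ties the form to the scheduled Day 1 visit, the Cycle 2 row does not apply the split, and a subject who is dosed on Day 1 and then stops has initiated the cycle yet still loses a form completed that day.

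Other points stand and limit the concern. The group is narrow: a form must be completed at the visit where treatment ends. Stoppers have their own End of Treatment row, and they would leave all later cycle means anyway, so the rule brings attrition forward by one visit.

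Four stronger readings are tempting but not supported:

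- *The planned rest week is the cause.* It is not. Under continuous dosing with a last dose on Day 56 the cap would be Day 55, and a Day 57 form would still be excluded. The rest week only widens the gap.
- *The loss is concentrated at Cycles 3, 5 and 7 because 8-weekly scans fall there.* This is plausible but not established. Scans have a ± 5 day window and keep their schedule regardless of dosing delays, so scans and cycles can drift apart.
- *The means are wrong by several points.* That needs a large share of all discontinuations to fall at a Day 1 visit with a form completed, together with a large deficit. The documents support neither.
- *The data are lost.* They are not. Every score is listed, and the EQ-5D-5L shift table uses the worst post-baseline record, not the cycle windows.

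**Conclusion.** The point holds as a defect in a stated analysis rule. From Cycle 3 on, SAP Table 2 selects by-visit quality-of-life data on a dosing decision made at or after the visit, and it treats Cycle 2 differently without a reason.

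The exclusion follows from the SAP's own day arithmetic and needs no assumption beyond a form completed at the stopping visit. The direction does rest on an assumption: the means are too favourable only if stoppers score worse (a QLQ-H&N35 mean too low, an EQ-VAS mean too high). The size is unknown. About 1 point on the 0–100 scale is an illustration, assuming 10% excluded and a 10-point deficit; larger figures need stronger assumptions.

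Quality of life is summarised descriptively with no test specified, so the objective response analysis and error control are untouched. It should be corrected because the correction is cheap, not because it threatens the trial's main conclusion.

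**What to change.** In SAP Table 2:

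1. Remove the last-dose cap for forms collected at a scheduled Cycle n Day 1 visit. Assign any form that the CRF records at that visit, within the visit window, to Cycle n whatever the last dose date.
2. Assign forms recorded at the End of Treatment visit to End of Treatment.
3. Use each form once.
4. Apply the same rule to Cycle 2 and all later cycles.

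Moving the cap to a fixed number of days after the last dose is not an adequate substitute. With a cap at last dose + 14, a subject whose Days 15–21 were not taken in Cycle 2 has a last dose on Day 35 and a cap at Day 49, so the Day 57 form is still dropped. Extended to Cycle 2, such a cap would newly drop the Day 29 form of a subject last dosed on Day 7 (cap Day 21).

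The cost is a few lines of SAP wording and a programming change, with no new data. It assumes that the CRF identifies the visit for each questionnaire, which the documents do not show. Cycle means may become slightly less favourable and will include some forms completed after the final dose; a table footnote should say so.

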### EORTC QLQ-H&N35

The European Organization for Research and Treatment of Cancer Quality of Life Questionnaire (EORTC QLQ)-H&N35 is a 35-item questionnaire module designed to assess the QoL of head and neck (H&N) cancer patients. It consists of 7 multiple-item scales (Pain, Swallowing, Senses, Speech, Social eating, Social contact, and Sexuality) and 11 single items. Scoring of EORTC QLQ-H&N35 will be computed following the procedures recommended in the Scoring Manual provided by EORTC Data Center ([Scott, N., Fayers, P., Aaronson, N., Bottomley, A., de Graeff, A., Groenvold, M., Gundy, C., Koller, M., Petersen, M.A. and Sprangers, M.A.G., 2008. EORTC QLQ-C30. Reference values. Brussels: EORTC. 2008](#)). For each multiple-item scale or single item, a linear transformation will be used to standardize the raw score to range between 0 and 100. The detailed scoring procedures are specified in [Appendix 2 Scoring Approach for EORTC QLQ-H&N35](#). For all items and scales, high scores indicate more problems.

Actual and change from baseline score in Pain, Swallowing, Speech Problems, and Senses Problems scales of EORTC QLQ-H&N35 will be summarized at each applicable post-baseline visits. The individual multiple-item scale or single item score at each visit will be listed.

## EQ-5D-5L

EQ-5D-5L is a health status measure questionnaire composed of 5 health questions (descriptive system) and a visual analog scale (EQ-VAS). The descriptive system covers 5 dimensions (mobility, self-care, usual activities, pain/discomfort, and anxiety/depression) with 5 levels of answer in each dimension (no problems, slight problems, moderate problems, severe problems and unable to perform/extreme problems). The EQ-VAS collects the self-rating health status from 0 (the worst imaginable health) to 100 (the best imaginable health).

Actual and change from baseline score of EQ-VAS will be summarized at each post-baseline visits. EQ-5D-5L results in each dimension and EQ-VAS at each visit will be listed.

A shift table from baseline to the worst post-baseline record for each dimension will be presented. Percentages for shift tables will be based on the number of subjects with a value at both baseline and at least 1 post-baseline visit.

## 9.8 Safety Analyses

Safety analyses will be performed using the safety analysis set, defined as all subjects who receive at least one dose of study drug (tipifarnib).

### 9.8.1 Adverse Events

All summaries of AEs will be based on treatment-emergent AEs (TEAEs) unless otherwise indicated.

TEAE is defined as AE that starts on or after the first dose of the study drug and within 30 days of the last administration of the study drug.

Counting of AEs will be by subject, not by event; subjects will be counted only once within each SOC or PT.

The count and percentage of subjects who report TEAEs will be summarized for AIM-HN safety analysis set as follows:

TEAEs by SOC and PT

TEAEs by PT (Any Grade and Grade  $\geq$  3)

TEAEs by SOC, PT, and maximum NCI-CTCAE grade

Serious TEAEs by SOC and PT

TEAEs related to tipifarnib by PT (Any Grade and Grade  $\geq$  3)

TEAEs related to tipifarnib by SOC, PT, and maximum NCI-CTCAE grade

Serious TEAEs related to tipifarnib by SOC and PT

TEAEs leading to discontinuation of tipifarnib by SOC and PT

TEAEs with an outcome of death by SOC and PT

Non-Serious TEAE experienced by  $\geq$  5% of subjects by PT

For grade summaries, subjects with multiple events within a particular SOC or PT will be counted under the category of their most severe event within that SOC or PT. Events will be sorted by descending frequency by SOC, and by PT within SOC for summaries.

AEs will be listed for individual subjects, including information regarding onset, duration, severity, seriousness, outcome and relationship to study drug.

AEs will not be summarized by Cycle, except for Overall Summary and AEs by SOC and PT for Cycle 1.

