7. Buccal swabs will be collected at screening for CXCL12 SNP testing and as a control sample for the analysis of tumor mutations using kits provided by the Sponsor. If swabs are not collected during screening for any reason, collection can be conducted at any time during the study. Detailed buccal swab collection, storage and shipping procedures will be provided in a separate lab manual.
8. Assessments of adverse events and concomitant medications may also be conducted if adverse events were not resolved at the time of the End of Treatment visit.
9. Assessed from signing the AIM-HN ICF through approximately 30 days after treatment discontinuation. Additional assessments may be performed until AE resolution or the AE is deemed irreversible by the Investigator.
10. Evaluation should be performed within 14 days prior to the first administration of study drug. Lab investigations (hematology and serum chemistry) should be repeated and reviewed within 72 hours of first dosing and continued eligibility for dosing confirmation.
11. Assessment on Cycle 1 Day 1 is to occur prior to tipifarnib dosing. Labs drawn within 72 hours of dosing may be used for CID1. Labs must be reviewed prior to dosing to confirm subject remains eligible.
12. Vital signs to include: heart rate, blood pressure and temperature.
13. In addition to baseline tumor scans that are to be obtained within 28 days prior to Cycle 1 Day 1, efforts should be made to obtain historical scans to document tumor progression on prior line of therapy for transfer to the IRF. All efforts to submit these scans by the first tumor response assessment (approximately 8 weeks following Cycle 1 Day 1) should be made. These historical scans should include the scans that demonstrate progression that occurred on the prior regimen and a prior scan demonstrating the nadir prior to the progression.
14. Pregnancy testing will be performed in females of child-bearing potential and testing may be performed on urine or serum. If a positive urine pregnancy test is obtained, a confirmatory serum pregnancy test should be conducted. If confirmatory test is positive, subject must terminate tipifarnib treatment immediately and follow pregnancy reporting guidelines outlined in the protocol. Pregnancy testing will be performed locally at the clinical site or its reference laboratory.

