 6. At least 2 weeks or 5 half-lives, whichever is longer, since the last systemic therapy regimen prior to Cycle 1 Day 1. Last dose of any prior checkpoint inhibitor therapy must have been administered at least 2 weeks prior to C1D1. Subjects must have recovered to NCI CTCAE v5.0 < Grade 2 from all acute toxicities (excluding Grade 2 toxicities that are not considered a safety risk by the Sponsor and Investigator) or toxicity must be deemed irreversible by the Investigator.
 7. At least 2 weeks since last radiotherapy. Subjects must have recovered from all acute toxicities from radiotherapy.
 8. ECOG performance status of 0-1 ([Appendix II](#)).
 9. Acceptable liver function:
 - a) Bilirubin ≤ 1.5 times upper limit of normal (x ULN).
 - b) AST (SGOT) and ALT (SGPT) ≤ 1.5 x ULN.

The subject must meet/continue to meet these criteria at the time of first dosing, as confirmed by analysis within 72 hours of C1D1.

10. Acceptable renal function with either serum creatinine ≤ 1.5 x ULN or a calculated creatinine clearance ≥ 60 mL/min using the Cockcroft-Gault or Modification of Diet in Renal Disease (MDRD) formulas.

The subject must meet/continue to meet these criteria at the time of first dosing, as confirmed by review of analysis performed within 72 hours of C1D1.

11. Acceptable hematologic status:
 - a) ANC ≥ 1000 cells/ μ L.
 - b) Platelet count $\geq 75,000$ / μ L.
 - c) Hemoglobin ≥ 8.0 g/dL.

The subject must meet/continue to meet these criteria at the time of first dosing, as confirmed by review of analysis performed within 72 hours of C1D1.

12. Female subjects must be:
- a) Of non-child-bearing potential (surgically sterilized or at least 2 years post-menopausal); or

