11.3 Adverse Event Reporting

11.3.1 Procedure for Reporting Adverse Events

The AE reporting period for safety surveillance begins when the subject is included into the study (date of first signature of AIM-HN informed consent) and continues through the study's post-treatment follow-up period, defined as approximately 30 days from the final administration of the study treatment or immediately before initiation of any other anticancer therapy, whichever comes first.

The Investigator is required to grade the severity/intensity of each AE. Investigators will reference the NCI-CTCAE v 5.0. This is a descriptive terminology that can be used for AE reporting. A general grading (severity/intensity) scale is provided at the beginning of the referenced document, and specific event grades are also provided. If a particular AE's severity/intensity is not specifically graded by the guidance document, the Investigator is to revert to the general definitions of Grade 1 through Grade 5 and use his or her best medical judgment.

The 5 general grades are:

- Grade 1: Mild

- Grade 2: Moderate
- Grade 3: Severe or disabling
- Grade 4: Life-threatening
- Grade 5: Death related to AE. Note: Death (Grade 5 as defined by NCI-CTCAE version 5.0) is mainly regarded as an outcome, to be documented as described below.

According to the Sponsor's convention, if a severity/intensity of Grade 4 or 5 is applied to an AE, then the Investigator must also report the event as an SAE as per [Section 11.4.2](#). However, a laboratory abnormality with a severity/intensity of Grade 4, such as low white blood cell count or increased ALT, is considered serious only if the condition meets one of the serious criteria described below.

In the case of death, the primary cause of death (the event leading to death) should be recorded and reported as an SAE. "Fatal" will be recorded as the outcome of this respective event; death will not be recorded as separate event. Only if no cause of death can be reported (e.g., sudden death, unexplained death), the death per se might be reported as an SAE.

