11.4.4 Events Not to Be Considered as AEs/SAEs

Medical conditions present at the initial study visit that do not worsen in severity or frequency during the study are defined as Baseline Medical Conditions and are NOT to be considered AEs. Progression of underlying disease is not an AE and therefore not an SAE per se, rather an efficacy endpoint, unless deemed to be causally related to administration of IP. However, if

adverse signs or symptoms occur in association with disease progression then these should be recorded as AEs and reported as SAEs if meeting any seriousness criteria.

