12.1.2 Safety and Tolerability

Safety and tolerability of tipifarnib will be assessed based on the following:

- Incidence, duration, and severity of treatment-emergent AEs, SAEs, AEs resulting in permanent discontinuation of study drug, and deaths within approximately 30 days from the last dose of study drug (or immediately before the administration of another anti-cancer treatment)
- Changes in laboratory test results
- Changes in vital signs including blood pressure, heart rate and temperature
- Changes in ECG results

AEs will be coded using the using version 22.0 of the Medical Dictionary for Regulatory Activities (MedDRA) and upversioned prior to database lock. Treatment-emergent AEs are defined as AEs that start on or after the first dose of study drug and within approximately 30 days of the last administration of study drug. AEs will be summarized by the number and percentage of subjects who experienced the event, according to system organ class and preferred term. A subject reporting multiple cases of the same AE will be counted once within each system organ class and similarly counted once within each preferred term.

Unless specified otherwise, the denominator for these calculations will be based on the number of subjects enrolled who received at least one administration of tipifarnib, irrespective of the total number of doses or treatment cycles administered. These conventions will be appropriately modified to calculate AE incidence rates separately for each cycle that study therapy is administered. AE incidence rates may also be calculated based on other measures of subject exposure (e.g., total number of treatment cycles administered). AEs will also be summarized by NCI CTCAE v5.0 severity grade and by relationship to each study drug. Additional summaries may also be provided for SAEs, and events resulting in the permanent discontinuation of therapy. All AEs will be included in individual subject listings.

The incidence of grade 3 and 4 hematological toxicities (including neutropenia, thrombocytopenia, and anemia) will be provided by treatment cycle and across all treatment cycles. The toxicity grades for laboratory tests will be based on NCI CTCAE v5.0. The use of blood transfusions (platelets, red blood cells) and/or growth factor support will be reported.

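### The treatment-emergent AE rule uses start date alone, so an AE that begins between consent and first dose and worsens on tipifarnib can be left out of the TEAE tables

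*SAP*

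**What the plan says.** The SAP rule, in 9.8.1, is that "TEAE is defined as AE that starts on or after the first dose of the study drug" and no later than 30 days after the last dose. Protocol 12.1.2 matches it, apart from making the 30 days approximate: "Treatment-emergent AEs are defined as AEs that start on or after the first dose of study drug". Neither text mentions an event that was already open at the first dose and then got worse, and no such clause appears elsewhere in the SAP.

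The rule has wide reach. SAP 9.8.1 adds: "All summaries of AEs will be based on treatment-emergent AEs (TEAEs) unless otherwise indicated". The tables listed there cover any grade, Grade 3 or higher, related, serious, leading to discontinuation, and fatal events.

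Collection starts earlier than the rule does. Protocol Table 2, footnote 9, says of AEs: "Assessed from signing the AIM-HN ICF through approximately 30 days after treatment discontinuation". Protocol 11.3.1 gives the same starting point. Screening runs up to 28 days before Cycle 1 Day 1, and the screening procedures in protocol 9.2.1 include AEs that are already ongoing.

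Protocol 11.4.4 removes from AE status only this group: "Medical conditions present at the initial study visit that do not worsen in severity or frequency during the study".

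**The concern.** The plan opens AE records before dosing but decides whether an event is treatment-emergent from its start date alone. An AE that begins in screening at a low grade and becomes severe on tipifarnib is on-treatment toxicity in any ordinary sense. If the site keeps it as one record, its start date precedes the first dose and the rule excludes it. Protocol 11.4.4 treats worsening as the thing that matters for a pre-existing condition, and the TEAE rule does not carry that principle through.

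The trial is single-arm and pivotal, so the TEAE tables are the main summary of tolerability and there is no control arm in which the same loss would occur. Two sites that record the same course of events differently would contribute differently to the same table.

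**Working it through.** Neither document gives a figure that depends on the TEAE rule, so there is nothing to reproduce. The check is to apply the rule to each way an event could be recorded, and then to show the scale.

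**Applying the rule.** Take fatigue that is Grade 1 before the first dose and Grade 3 during treatment.

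| How it is recorded | Start date used | TEAE? |
|---|---|---|
| Began after consent; one record, grade updated | Before first dose | No |
| Began after consent; new record opened at the grade change | After first dose | Yes |
| Present at the initial study visit and stable, so not an AE under protocol 11.4.4; becomes an AE on worsening | Naturally the date of worsening | Yes |
| Start date wholly missing | Imputed to first dose date (SAP 8.1.1) | Yes |

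The first two rows are the same clinical event with opposite results. Protocol 11.2 asks for unfavourable changes in the subject's condition to be recorded as AEs, with onset date, resolution date and severity. It does not say whether a grade increase in an open AE starts a new record, and it leaves detail to eCRF conventions that are not among the documents. Which row applies therefore cannot be settled from the protocol and SAP.

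The last row does not repair the gap. A screening AE with no date counts as treatment-emergent even if it never worsens, while a correctly dated one that worsens may not count.

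**Direction.** The first row can remove a subject from a table and cannot add one. For this mechanism the error is downward only.

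**Which terms are exposed.** Protocol 4.3 names haematological events, nausea, vomiting, diarrhoea and fatigue as the most common AEs.
- Haematological: protocol 11.4.5 keeps most abnormal laboratory findings from being AEs at all. Protocol 12.1.2 calls for Grade 3 and 4 haematological toxicity by cycle and overall. SAP 9.8.3 gives shifts from baseline grade to maximum post-baseline grade for some haematology and chemistry tests. These routes do not use AE start date.
- Deaths: SAP 9.8.2 tabulates them, with causes, from the survival status form.
- Fatigue, nausea, vomiting, diarrhoea: no summary table outside the TEAE set. The AE listings show onset and severity subject by subject but give no rates.

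**Scale.** Let N be the number treated, n the number who should be counted for a term, and k the number lost. A subject is lost only if no other record of that term qualifies for the same table. The reported rate is (n − k)/N, so the shortfall is k/N. With the planned minimum N = 80 (protocol 6.2):
- k = 1: 1/80 = 1.25 percentage points
- k = 8: 8/80 = 10 percentage points
- The table of non-serious TEAEs in at least 5% of subjects needs 0.05 × 80 = 4 subjects. A term with exactly 4 that loses one shows 3/80 = 3.75% and drops off the table.

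The range of k from 1 to 8 is illustrative; the documents give no count of screening AEs that worsen. SAP Section 3 mentions early closure, so N may be below 80, in which case each loss weighs more.

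**The case against.** The strongest reply is that sites may already open a new AE record when a grade rises. Protocol 11.2 and 11.4.4 can be read that way, and if it was done throughout, nothing is lost. This stands as a limit on the claim, but it does not answer it: the documents do not state the convention, and a safety definition should not rest on an unstated one.

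A reader might infer three stronger things, and none is supported.

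- *Such events drop out of every TEAE table.* Whether they drop out at all depends on how the worsening is recorded, as shown above.
- *The loss is common here because entry is permissive.* The criteria allow an ANC of 1000/µL, platelets of 75,000/µL, haemoglobin of 8.0 g/dL and residual toxicity, "excluding Grade 2 toxicities that are not considered a safety risk by the Sponsor and Investigator". But low counts and residual toxicity usually predate consent. Under protocol 11.4.4 they become AEs only on worsening, and their natural onset is then after the first dose. The clearly exposed group is narrower: AEs arising between consent and first dose.
- *Severe haematological toxicity is materially under-reported.* A mild laboratory abnormality at screening would ordinarily open no AE record, and severe haematological toxicity has its own reporting routes.

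It is also fair to say that the listings would let a careful reader find individual cases. That helps case review and leaves the rates unchanged.

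**Conclusion.** The definition in SAP 9.8.1 and protocol 12.1.2 has a real gap. As written, it excludes an AE that began between consent and first dose and worsened in CTCAE grade on tipifarnib, provided the site kept it as one record. The affected tables are any grade, Grade 3 or higher, related, serious, and leading to discontinuation. The exposure is mainly in non-laboratory terms.

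The amount is unknown and may be nil. It rests on two things the documents do not give: how many screening AEs worsened, and how sites dated the worsening. If 80 subjects are treated, each subject lost costs 1.25 percentage points. No particular understatement of a Grade 3 or higher rate can be claimed. The point does not touch the primary endpoint, but the correction is cheap enough that it should be made.

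**What to change.** In SAP 9.8.1, in a version approved before database lock, define a TEAE as an AE that starts, or worsens in CTCAE grade relative to its pre-dose state, from the first dose through 30 days after the last. Note the difference from protocol 12.1.2 in SAP Section 3.

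In programming, flag AEs with a pre-dose start that were ongoing at Cycle 1 Day 1 and whose on-treatment grade exceeds the pre-dose grade. Where the AE page holds only one grade per record, query the sites once for those AEs. A clause on causality is not needed, because relationship is assessed for whichever events qualify.

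If the eCRF conventions already required a new record for every post-dose grade increase and sites followed them, stating that in the SAP would be enough.

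The cost is one sentence, one derived flag and a small query round. TEAE rates may become slightly less favourable.
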